8.3.6. Pregnancy Reporting

If a female participant becomes pregnant during the trial, the participant should inform the trial site as soon as possible. Upon confirmation of the pregnancy, the female participant will be discontinued from the trial. If a female partner of a male participant becomes pregnant, the participant should inform the trial site as soon as possible. The Investigator must complete a trial-specific pregnancy form upon confirmation of a pregnancy and send it to the pharmacovigilance unit within 24 hours of confirmation of the pregnancy (contact information to be used is the same

as for SAE reporting). The pharmacovigilance unit will report all cases of pregnancy to the medical monitor, the Sponsor, and the CRO in a timely manner until completion of the pregnancy, until a healthy live-born offspring, or until the outcome of any abnormality. Pregnancy is not itself an AE or SAE; however, maternal/fetal complications or abnormalities will be recorded as AEs or SAEs, as appropriate. The Investigator will follow the pregnancy until completion or until pregnancy termination and, in the case of a live-born offspring, to 1 month of age in that infant. The Investigator will notify the pharmacovigilance unit and the CRO of the outcome as a follow-up to the initial pregnancy form. All pregnancies should be reported to the Sponsor and, when applicable, to the ethics committee.

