The first day of dosing is considered Day 1. To reduce the risk of unblinding to the study personnel who will be evaluating the participant, study intervention will be administered by an unblinded pharmacist/IP Manager or a study site staff member who is not otherwise involved in the participant's participation in the study. The study intervention administrator should be experienced in performing SC injections. The skin surface of the anterolateral thigh, upper outer triceps area, upper buttocks, or abdomen (avoiding a 2-inch [5 cm] radius around the umbilicus) should be prepared with an alcohol wipe and allowed to air dry. The skin will be pinched to isolate SC tissue from the muscle. The needle will be inserted at a 90-degree angle to the skin surface approximately halfway into the SC tissue. The prepared study intervention will be slowly injected (at least a 5 second duration is recommended per 1.5 mL syringe) into the SC tissue using gentle pressure. The area should not be massaged after injection. The SC injection site may be changed during the study as per the participant's preference.

Further guidance and information for the preparation and administration of study intervention are provided in the Pharmacy Manual.

Duration of Treatment and Follow-up:

Screening: Completed within 28 days prior to the Day 1 Visit.

Double-Blind Treatment Period (Day 1 through [REDACTED]) Study treatment (daxdilimab or placebo) is administered SC [REDACTED] with an additional dose [REDACTED], all participants will be assigned to a quarterly dosing maintenance regimen based upon the renal response observed at [REDACTED] and will either receive daxdilimab or placebo [REDACTED] (last dose administered at [REDACTED]). Final evaluation will occur at [REDACTED].

End-of-Study/Early Termination Visit: Week 112 or earlier if the participant withdraws consent to participate in the trial.

Safety Follow-Up: Participants should be followed to assess AE/SAEs for at least 12 weeks after the last study intervention administration, approximately 4, 8, and 12 weeks after the last study intervention dose, unless the participant withdraws consent. Participants who do not agree to in-person follow-up site visits will be contacted (through telehealth visits – video call/phone/email) to assess AE/SAEs, unless the participants withdraw consent. Assessments will include of any AE/SAEs that have occurred within the last 4 weeks and will confirm if any previous AE/SAEs have resolved.

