7.1. Discontinuation

Any participant who decides to discontinue from the trial prematurely and does not plan to participate in the post-treatment SFU Period will be requested to complete the ET Visit.

Participants who discontinue will not be replaced.

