Participants who prematurely stop dosing prior to Week 52 will be followed for regularly scheduled visits through Week 52 unless participants withdraw consent of trial participation (See Section 7.1.3) or are lost to follow-up (See Section 7.2). Participants should be followed to assess AE/SAEs for at least 12 weeks after the last study intervention administration, approximately 4, 8, and 12 weeks after the last study intervention dose, unless the participant withdraws consent.

Participants who prematurely stop dosing after Week 52 but remain in the study will be complete the EOT Visit and the SFU Period, unless the participant withdraws consent. Participants will not automatically be removed from the trial if any administration of study intervention is missed.

Early discontinuation of study intervention for reasons other than lack of efficacy

An individual participant will not receive any further study intervention if any of the following occur in the participant:

- Receipt of Prohibited Medications (See Section 6.7.2).
- A Common Terminology for Adverse Events (CTCAE v5.0 dated 27 NOV 2017) Grade 3 or higher allergic reaction to the study intervention.
- A CTCAE Grade 3 or higher infection considered related to the study intervention.
- Other AE that contraindicates further dosing in the opinion of the Investigator and/or the Sponsor, or Medical Monitor.

- Withdrawal of consent from further treatment with study intervention.
- Participant is determined to have met one or more of the exclusion criteria or failed to meet all the inclusion criteria for study participation and there is a potential safety risk associated with continuation identified upon consultation with the Medical Monitor.
- Pregnancy or a decision to become pregnant.
- Any of the following liver function abnormalities:
 - alanine aminotransferase (ALT) or aspartate aminotransferase (AST) $\geq 8 \times$ ULN.
 - ALT or AST $\geq 5 \times$ ULN for more than 2 weeks.
 - ALT or AST $\geq 3 \times$ ULN and total bilirubin $\geq 2 \times$ ULN.
 - ALT or AST $\geq 3 \times$ ULN with the appearance of fatigue, nausea, vomiting, right upper quadrant pain or tenderness, fever, rash, and/or eosinophilia ($\geq 5\%$).

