Participants who prematurely stop dosing prior to Week 52 will be followed for regularly scheduled visits through Week 52 unless participants withdraw consent of trial participation (See Section 7.1.3) or are lost to follow-up (See Section 7.2). Participants should be followed to assess AE/SAEs for at least 12 weeks after the last study intervention administration, approximately 4, 8, and 12 weeks after the last study intervention dose, unless the participant withdraws consent.

Participants who prematurely stop dosing after Week 52 but remain in the study will be complete the EOT Visit and the SFU Period, unless the participant withdraws consent. Participants will not automatically be removed from the trial if any administration of study intervention is missed.

Site Investigators will be trained about the importance of retention of participants through the completion of the study, and participants will be informed about the continued scientific importance of their data even if they discontinue study intervention early.

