8.3.3. Time Period and Frequency for Event Assessment and Follow-Up

The occurrence of an AE or SAE may come to the attention of trial personnel during trial visits and interviews of a trial participant presenting for medical care, or upon review by a trial monitor.

All AEs, including local and systemic reactions, will be captured on the appropriate eCRF. Information to be collected includes event description, date of onset, clinician's assessment of severity, relationship to study intervention (assessed only by those with the training and authority to make a diagnosis), and date of resolution/stabilization of the event. All AEs occurring while on trial must be documented appropriately regardless of relationship.

Trial site personnel will note the occurrence and nature of each participant's medical condition(s) present prior to the informed consent signature in the appropriate section of the source document and eCRF. During the trial, site personnel will note any change in the condition(s) and the occurrence and nature of any AE.

Any medical condition that is present prior to informed consent signature will be considered as part of medical history and not reported as an AE. However, if the trial participant's condition deteriorates after the consent signature, it will be recorded as an AE.

Should a participant experience an AE at any time after the informed consent signature until the end of participation in the trial, the event will be recorded as an AE in the source document and eCRF. Any SAE related to the trial participation (eg, screening procedure) will be recorded in the source document and eCRF from the time consent is given to participate in the trial until the end of participation in the trial.

The Investigator is responsible for appropriate medical care of participants during the trial. The Investigator also remains responsible for following through with an appropriate health care option for all AEs that are ongoing at the end of the trial. The participant should be followed until the event is resolved or stable. If an AE is ongoing at the end of trial, the follow-up duration is left to the discretion of the Investigator. Follow-up frequency will be performed at the discretion of the Investigator.

Whenever possible, clinically significant abnormal laboratory results are to be reported using the diagnostic that resulted in the clinically significant abnormal laboratory results and not the actual abnormal test.

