8.3.5. Serious Adverse Event Reporting

Horizon Therapeutics Ireland DAC will be the pharmacovigilance unit responsible for the overall pharmacovigilance process for this trial. All SAEs, related to the experimental treatment or not, occurring during the course of the trial must be reported by entering the information into the eCRF on an SAE form to the pharmacovigilance unit (see below contact information) within 24 hours of the knowledge of the occurrence (this refers to any AE that meets one or more of the aforementioned seriousness criteria). The SAE reporting period ends at the end of the Follow-Up Period or if the participant begins an alternative therapy.

Reporting should be done by sending the completed SAE form to the following e-mail address (faxing may also be done as a second option in case e-mailing is not possible).

Safety Contact Information: Horizon Therapeutics

E-mail: [contact]

US [contact]

The pharmacovigilance unit will inform the Medical Monitor, the Sponsor, and the Contract Research Organization (CRO) within 1 business day of awareness of a new SAE. The pharmacovigilance unit will process and evaluate all SAEs as soon as the reports are received. For each SAE received, the pharmacovigilance unit, in consultation with the Sponsor if needed, will make a determination as to whether the criteria for expedited reporting to relevant regulatory authorities have been met.

The expedited reporting of relevant safety information to concerned regulatory agencies and ethic committees will be performed in accordance with local laws and regulations and will be defined in the Safety Management Plan.

The trial Sponsor will be responsible for notifying the Food and Drug Administration (FDA) of any unexpected fatal or life-threatening suspected adverse reactions as soon as possible, but in no case later than 7 calendar days after the Sponsor's initial receipt of the information. In addition, the Sponsor must notify the FDA and all participating Investigators in an Investigational New Drug (IND) safety report of potential serious risks, from clinical trials or any other source, as soon as possible, but in no case later than 15 calendar days after the Sponsor determines that the information qualifies for reporting.

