9.4.3. Secondary Endpoints Analysis

The estimand for the binary secondary efficacy endpoints is defined as follows, using composite variable strategy to address intercurrent events.

1. Population:
 - a. ORR: Participants in the Full Analysis Set.
 - b. Sustained reduction of OCS dose: Participants in the Full Analysis Set whose Baseline OCS dose is greater than 2.5 mg/day prednisone equivalent.
2. Variable (outcome measure):

- a. ORR at [REDACTED] which is an CRR or PRR at Week 52. PRR is defined by meeting the following criteria:
 - i. eGFR ≥ 60 mL/min/1.73m² or no worse than 15% below baseline.
 - ii. Improvement in 24-hour UPCR:
 - For participants with a baseline UPCR ≤ 3.0 mg/mg: < 1.0 mg/mg
 - For participants with a baseline UPCR > 3.0 mg/mg: $> 50\%$ improvement from baseline and ≤ 3.0 mg/mg
 - iii. No use of restricted medication beyond the protocol allowed threshold before assessment.
 - iv. No discontinuation of study intervention.
- b. Response in sustained reduction of OCS dose, which is defined by meeting the following criteria:
 - i. Prednisone-equivalent dose ≤ 2.5 mg/day by Week 24 and not exceeding this dose through Week 52.
 - ii. No use of restricted medication beyond the protocol allowed threshold before assessment.
 - iii. No discontinuation of study intervention.
3. Intercurrent event:
 - a. Rescue medications: Captured in the variable definition.
 - b. Treatment discontinuation: Captured in the variable definition.
4. Population-level summary: Difference in proportions of responders between the daxdilimab group and placebo group.

ORR will be analyzed using a logistic regression model with treatment, baseline eGFR value and baseline UPCR value included in the model. Response in sustained reduction of OCS dose will be analyzed similarly using a logistic regression model with treatment, randomization stratification factors and baseline OCS dose included in the model.

The estimand of change from baseline in eGFR at Week 52 is defined as follows, using hypothetical strategy to address intercurrent event of rescue medications and treatment policy strategy to address intercurrent event of treatment discontinuation.

1. Population: Participants in the Full Analysis Set.
2. Variable (outcome measure): Change from baseline in eGFR at Week 52.
3. Intercurrent event:
 - a. Rescue medications: The data collected after administration of the rescue medications will be excluded.

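### Section 8.3.6 takes a pregnant participant out of the trial, whereas Section 7.1.1 stops only her study treatment and keeps her in follow-up

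*Protocol*

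**What the plan says.** Protocol Section 8.3.6 deals with a participant who becomes pregnant: "Upon confirmation of the pregnancy, the female participant will be discontinued from the trial". It then requires the pregnancy to be followed to its outcome and a live-born infant to 1 month of age, with maternal or fetal complications recorded as AEs or SAEs.

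Protocol Section 7.1.1 lists "Pregnancy or a decision to become pregnant" among the events after which a participant receives no more study intervention. For participants who stop dosing it then requires:

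- scheduled visits through Week 52 if dosing stops before Week 52, except after withdrawal of consent or loss to follow-up;
- the end-of-treatment (EOT) visit and the Safety Follow-Up (SFU) Period if dosing stops later, except after withdrawal of consent;
- safety contacts: "Participants should be followed to assess AE/SAEs for at least 12 weeks after the last study intervention administration", at about 4, 8 and 12 weeks, except after withdrawal of consent.

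None of these rules has a pregnancy exception.

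Two other sections set when recording ends. Section 8.3.3 ties AE recording to participation: "Should a participant experience an AE at any time after the informed consent signature until the end of participation in the trial". Section 8.3.5 sets the SAE limit: "The SAE reporting period ends at the end of the Follow-Up Period or if the participant begins an alternative therapy".

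**The concern.** Stopping treatment and leaving the trial are separate events in this protocol. They have separate sections (7.1.1 and 7.1.2), and SAP Section 4.5 reports them on separate disposition lines. The words in 8.3.6 therefore cannot safely be read as shorthand for stopping treatment, and no sentence says which section governs a pregnant participant.

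Two sites facing the same event could act differently. One would keep the participant in visits and contacts. The other would close her participation and, under 8.3.3, stop recording AEs that are not pregnancy complications. Those could include infection, hypersensitivity or malignancy, all named as important potential risks in Section 2.2.1. The second site would also lose laboratory data after discontinuation that some planned analyses use.

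**Working it through.** The check is mainly a comparison of text. The plan states no figure on this point to reproduce.

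**Step 1. The two rules side by side.**

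| Item | Following 7.1.1 | Following 8.3.6 literally |
|---|---|---|
| Study intervention | Stopped | Stopped |
| Visits, dosing stopped before Week 52 | Continue through Week 52 | End at confirmation, apart from an early termination visit |
| Dosing stopped after Week 52 | EOT visit and SFU Period | Not provided for |
| AEs unrelated to the pregnancy | At least 12 weeks after last dose | Until participation ends (8.3.3) |
| SAEs | Limit in 8.3.5 | Same limit in 8.3.5 |
| Pregnancy outcome, complications, infant | Followed (8.3.6) | Followed (8.3.6) |

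The rules differ on visits and on AEs unrelated to the pregnancy. They do not differ on the stated SAE limit or on pregnancy follow-up.

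**Step 2. Length of follow-up at stake.** Suppose pregnancy is confirmed at week w, before Week 52 and close to the last dose. Under 7.1.1 the remaining follow-up is at least max(52 − w, 12) weeks:

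- w = 12: max(40, 12) = 40 weeks
- w = 24: max(28, 12) = 28 weeks
- w = 48: max(4, 12) = 12 weeks

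Under the literal reading of 8.3.6 with 8.3.3, general AE recording lasts 0 further weeks.

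**Step 3. Safety contacts at stake.** Contacts fall about 4, 8 and 12 weeks after the last dose. If confirmation comes less than 4 weeks after that dose, 3 remain; at 4 to 8 weeks, 2; at 8 to 12 weeks, 1; later, none.

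**Step 4. Effect on the analyses.**

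- *Composite CRR, ORR and OCS reduction (SAP 4.8.1.1 and 4.8.2.1).* Stopping study intervention before assessment already makes the participant a non-responder. The result is the same under either section.
- *Change in eGFR at Week 52 (Protocol 9.4.3, SAP 4.8.2.1).* Treatment discontinuation is handled by treatment policy, so values after stopping are meant to be included. A literal 8.3.6 removes them for any pregnancy confirmed before Week 52.
- *Rescue exclusion.* For this estimand, "The data collected after administration of the rescue medications will be excluded". That does not make the missing eGFR values irrelevant. Section 6.7.6 presents rescue as therapy for worsening LN, and a change of background therapy made because of pregnancy is not clearly rescue.
- *Supplementary analyses (SAP 4.8.1.6 and 4.8.2.3).* These include observed data after treatment discontinuation, so they too lose data. With 70 per arm, one participant moves an arm's crude CRR or ORR proportion by at most 1/70 = 1.4 percentage points.
- *Safety and disposition tables.* SAP Table 5 sets no end date for treatment-emergent AEs in participants not dosed in Stage II, so what is counted depends on when the site stops recording. The treatment-discontinuation line is filled under either reading; the trial-discontinuation line depends on which section the site followed.

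**The case against.** The strongest reply is that the sections can be read together. Section 8.3.6 is the more specific rule and adds a further step for confirmed pregnancy. The reasons for leaving the trial in 7.1.2 are introduced as an inclusive list, so pregnancy's absence there proves nothing. The 12-week AE/SAE rule appears several times and is waived only for withdrawn consent, which pregnancy is not. Section 7.1 describes "Any participant who decides to discontinue from the trial prematurely and does not plan to participate in the post-treatment SFU Period", which implies that some who leave the trial may still enter safety follow-up. The synopsis adds remote contact: "Participants who do not agree to in-person follow-up site visits will be contacted".

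Much of this stands. It makes loss of the 12-week safety contacts possible rather than certain. It does not settle the matter: 7.1 is written for participants who choose to leave, the synopsis states a general rule without saying that it applies after removal under 8.3.6, and the Week 52 visits conflict directly with removal from the trial.

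Two stronger readings are tempting. A reader might infer that SAE reporting is cut short by 8.3.6. The documents do not support that: the limit in 8.3.5, including the start of alternative therapy, is the same whichever section a site follows, and leaving the trial is not itself a stated trigger. A reader might also use the 13 to 20 day half-life in Section 2.2.1 to gauge how many AEs would be missed. Residual drug does not measure lost events, and those half-lives come from single doses and take no account of accumulation over repeated dosing.

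**Conclusion.** The inconsistency is real and lies in operative text, but it is minor. A site following 8.3.6 literally could stop recording AEs unrelated to the pregnancy and skip visits whose data feed the Week 52 eGFR estimand and the treatment-policy supplementary analyses.

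It would go too far to infer that the efficacy conclusions are at risk. The composite CRR, ORR and OCS results do not change, and only pregnancies confirmed before Week 52 can affect the Week 52 eGFR analysis. The documents give no pregnancy rate, participants of childbearing potential who are sexually active with a non-sterilized male partner must use highly effective contraception, and women intending pregnancy are excluded. No number of affected participants can be stated.

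The conclusion rests on sites reading 8.3.6 as written. Manuals outside these two documents might already tell them otherwise.

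**What to change.** In Section 8.3.6, replace the removal from the trial with wording such as: *discontinued from study intervention and, with her consent, followed per Section 7.1.1, with no requirement to continue protocol MMF/MPA, in addition to the pregnancy follow-up below*. Section 7.1.1 then stays as it is.

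The MMF/MPA clause is a clarification. Table 3 schedules MMF/MPA dispensing at every first-year treatment visit, and keeping a pregnant participant in follow-up should not be read as obliging her to take it. Section 6.7.4.1.1 already allows MMF/MPA to be withheld for safety without a deviation.

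If the sponsor prefers to end scheduled visits at confirmed pregnancy, 8.3.6 should say that the 4-, 8- and 12-week AE/SAE contacts continue, and 7.1.1 needs a matching pregnancy exception to the Week 52 visits. That option gives up the later eGFR data.

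The first option costs one sentence and adds no procedure beyond those in 7.1.1. The second edits two sections.

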8.3.7. Overdose

Investigational Product overdose is any accidental or intentional use of study intervention in an amount higher than the dose indicated per protocol for a given participant. Study intervention compliance (see Section 6.5) should be reviewed to detect potential instances of overdose (intentional or accidental).

Any study intervention overdose during the trial should be recorded on the source document and eCRF. In the event of overdose, the participant should be closely monitored for any potential AEs. All AEs associated with an overdose should be entered on the Adverse Event eCRF and reported using the procedures detailed in Section 8.3.5, Serious Adverse Events Reporting, even if the events do not meet seriousness criteria. If the AE associated with an overdose does not meet seriousness criteria, it must still be reported using the SAEs reporting procedures and in an expedited manner but should be noted as non-serious on the form and the Adverse Event eCRF. The excess quantity and duration of the overdose should be recorded.

